6.2.4 Adverse Events

Any adverse event (AE) recorded on treatment including within 30 days from the last study treatment will be classified as treatment-emergent AE (TEAE) and will be summarized.

A drug-related TEAE is defined as any TEAE with at least possible relationship (possibly or probably related) to study treatment as assessed by the investigator or with missing assessment of the causal relationship

Serious adverse events (SAEs) include adverse events that are flagged as serious by the investigator or sponsor on eCRF, or upgraded by the Sponsor based on review of the Sponsor's list of Always Serious term.

Adverse events of special safety interest (AESI) are defined in the Safety Review Plan for ASP2215.

6.2.5 Other Variables

- Clinical laboratory variables (hematology, chemistry, coagulation, urinalysis, serum pregnancy test and bone marrow)
- Vital signs (systolic and diastolic blood pressure, pulse rate and body temperature)
- 12-lead electrocardiogram (ECG)
- Eastern Cooperative Oncology Group (ECOG) performance status scores

6.3 Pharmacokinetics Variables

Gilteritinib trough plasma concentrations (C_{trough}) samples will be collected for all subjects predose (within 1 h of dose administration) on cycle 1/day 1, 8 and 15, and on days 1 and 15 of each subsequent cycle up to 6 months.

6.4 Pharmacodynamics Variables

Blood samples for FLT3 and AXL will be collected on cycle 1/day 1 predose and postdose at 2 h, between 4 to 6 h, and 24 h. Changes in the activation status of FLT3 and AXL, a receptor tyrosine kinase (RTK), may be assessed before and after treatment.

6.5 Other Variables

- Body Mass Index (BMI)

$$\text{BMI} = \text{weight (kg)} / [\text{height (m)}]^2$$

- Duration of exposure

Duration of exposure to a study drug will be calculated in days, using the following formula:

Date of last dose of study drug – Date of first dose + 1 – number of days without drug administration in between.

When the start or stop date is missing, then the exposure will be treated as missing.

- Number of dosing days is defined as the number of days with non-zero dosing
- Cumulative Dose

Cumulative dose (mg) = sum of all doses of study drug taken during the study.

- Average daily dose is defined as (cumulative dose)/(number of dosing days) in “mg/day”
- Dose intensity is defined as (cumulative dose/duration of exposure) in “mg/day” for Gilteritinib and (cumulative dose/duration of exposure*14 days for Atezolizumab.
- Relative dose intensity is defined as (dose intensity/planned dose intensity)*100%.
- Treatment compliance

Treatment compliance of Gilteritinib is defined as:

Total number of doses of gilteritinib actually taken by the number of study drug expected to be taken during the study multiplied by 100.

Treatment compliance of Atezolizumab is defined as:

Total amount of Atezolizumab actually consumed by amount of study drug should be taken multiplied by 100.

- Duration of AML

Duration of AML will be calculated in days using the following formula:

$$(\text{Enrollment date} - \text{date of initial diagnosis of AML}) + 1$$

- Previous and concomitant medication

Previous medication is defined as medication with at least one dose taken before the date of the first dose of study drug.

Concomitant medication is defined as medication with at least one dose taken between the date of first exposure (inclusive) and the date of last exposure (inclusive) of study

drug. The first exposure is from 28 days prior to cycle 1 day 1. The last exposure date is max (the last dosing date for study drug, initial dosing date of the last cycle + 30).

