5.1.3.1 Additional Dosing Interruption Guidelines

- Cycle 1: If the cycle 1/day 15 dose of atezolizumab is withheld due to, a treatment-related AE then the cycle 1/day 15 dose should be skipped and atezolizumab administration resumed at day 1 of the next cycle, if the treatment-related event has resolved or returned to grade 1.
- Subsequent cycles 2 and beyond: if the day 1 and/or day 15 dose of atezolizumab in a cycle is delayed due to a treatment-related AE, then atezolizumab administration should be skipped until the next scheduled atezolizumab dose (e.g., day 1 or day 15) of a cycle.

- In subsequent cycles, atezolizumab and gilteritinib may be interrupted for situations other than treatment related AEs such as medical/surgical events or logistical reasons not related to study therapy. Subjects should be placed back on study therapy within 14 days of the scheduled interruption, unless otherwise discussed with the medical monitor. The reason for interruption should be documented in the subject's study record.

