7.3.7 Extent of Exposure

Drug exposure including duration of exposure, cumulative dose, average daily dose, dose intensity and relative dose intensity will be summarized by treatment group. The number and

proportion of subjects with dose reduction, dose escalation and dose interruption will be tabulated. Details of the calculation will be provided in SAP.

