7.3 Study Drugs

7.3.1 Exposure

The following information on drug exposure will be presented for the SAF:

- Descriptive statistics for cumulative amount of the drug subject was exposed to and average daily dose; and
- Number and percent of subject with dose increase, decrease or interruptions.

Duration of exposure will be summarized in two ways.

- Descriptive statistics will be presented.
- Exposure time will be categorized according to the following categories:
 - less than 3 months
 - at least 3 months, less than 6 months
 - at least 6 months, less than 12 months
 - at least 12 months, less than 24 months
 - 24 months or more
 - Unknown.

Counts and percentages of subjects in each of these categories will be summarized for the SAF.

Listing of subjects with dose reduction and interruption will also be provided for SAF.

Descriptive statistics for duration of exposure, cumulative amount of the drug subject was exposed to average daily dose, dose intensity and relative dose intensity will be presented for study drug.

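### The SAP's duration of exposure is just the count of dosing days, so atezolizumab dose intensity cannot show skipped infusions and gilteritinib dose intensity repeats average daily dose

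*SAP*

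**What the plan says.** Protocol 7.3.7 asks for several distinct exposure measures: "Drug exposure including duration of exposure, cumulative dose, average daily dose, dose intensity and relative dose intensity will be summarized by treatment group". It leaves the calculations to the SAP, so SAP 6.5 is the only definition.

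SAP 6.5 gives one duration formula for a study drug: last dose date minus first dose date plus 1, minus the "number of days without drug administration in between". It separately defines the number of dosing days as days with a non-zero dose. The derived measures are:

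- Average daily dose: "Average daily dose is defined as (cumulative dose)/(number of dosing days", in mg/day.
- Dose intensity, gilteritinib: cumulative dose over duration of exposure, in mg/day.
- Dose intensity, atezolizumab: "cumulative dose/duration of exposure*14 days for Atezolizumab". The bracket opened before this expression is never closed.
- Relative dose intensity (RDI): "Relative dose intensity is defined as (dose intensity/planned dose intensity)*100", as a percentage. Planned dose intensity is not defined.

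SAP 7.3.1 reports these as separate items ("Descriptive statistics for duration of exposure, cumulative amount of the drug subject was exposed to average daily dose, dose intensity and relative dose intensity") and also puts duration into bands ("Exposure time will be categorized according to the following categories") that run from under 3 months to 24 months or more. On missed infusions, protocol 5.1.3.1 says that from cycle 2, when a dose is delayed for a treatment-related AE, "atezolizumab administration should be skipped until the next scheduled atezolizumab dose". A withheld cycle 1 day 15 dose is likewise skipped.

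**The concern.** Subtracting every day without dosing from the span leaves only the days with dosing. For a daily drug, dose intensity then loses its time component and becomes the mean dose on days when drug was taken. For a drug infused once in 14 days, the subtraction removes the planned intervals themselves, and the factor of 14 is applied to a denominator that is no longer elapsed time.

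Safety and tolerability of the combination is a primary objective. The protocol's atezolizumab modification table has no dose-reduction step: doses are withheld, stopped, or the infusion is interrupted or slowed. Apart from a partly delivered infusion, a skipped one is the main way atezolizumab intensity could fall, and this formula cancels exactly that. The exposure tables would misdescribe how much of the combination was delivered and would disagree with the compliance table.

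**Working it through.** The documents state no numerical result for these measures, so there is no figure to reproduce. The check applies the SAP 6.5 formulas to example dosing records.

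**Inputs.** Atezolizumab 840 mg every 14 days (protocol 5.1.1.3; 420 mg scales identically). Gilteritinib once daily at 120 or 80 mg (protocol 5.1.1.1). Assumed: planned intensity is one assigned dose per 14 days (atezolizumab) or per day (gilteritinib), and 3 months is 91 days.

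**Identity.** Span = dosing days + off-drug days. Duration = span − off-drug days = dosing days.

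**Atezolizumab, k infusions on schedule.** Span = 14(k−1)+1; off-drug days = 13(k−1); duration = k.

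- Bracket read as (cumulative/duration)×14: 840k/k×14 = 11,760 mg per 14 days; RDI = 11,760/840 = 1400% for any k.
- Bracket read as cumulative/(duration×14): 840k/(14k) = 60 mg/day; against a planned 840/14 = 60 mg/day, RDI = 100% for any k.

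**Twelve scheduled infusions (span 155 days).**

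| | 12 given | 8 given (first and last included) |
|---|---|---|
| Off-drug days | 143 | 147 |
| Duration as written | 12 days | 8 days |
| Cumulative dose | 10,080 mg | 6,720 mg |
| RDI, first bracket reading | 1400% | 6,720/8×14 = 11,760, so 1400% |
| RDI, second bracket reading | 100% | 6,720/(8×14) = 60, so 100% |
| RDI over elapsed time (154+14 = 168 days) | 10,080/168×14 = 840, so 100% | 6,720/168×14 = 560, so 66.7% |

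**If only unplanned gaps are subtracted.** On-schedule RDI = 14k/(14(k−1)+1): 28/15 = 186.7% for 2 infusions, 56/43 = 130.2% for 4, 168/155 = 108.4% for 12. The excess arises because the interval after the last infusion is left out. With four of 12 skipped and 14 days removed per skip: 155−56 = 99 days; 6,720/99×14 = 950 mg; 950/840 = 113%. Intensity rises when infusions are missed.

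**Duration bands.** As written, a subject needs 91 infusions to reach 91 days of exposure. Those span 14×90+1 = 1,261 days, about 3.5 years.

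**Gilteritinib, constant 120 mg, 14 of 56 days missed.** Cumulative dose 42×120 = 5,040 mg. As written: 5,040/42 = 120 mg/day (100%), the same as average daily dose. Over elapsed time: 5,040/56 = 90 mg/day (75%).

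**Gilteritinib, 28 days at 120 mg then 56 days at 80 mg.**

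| | As written | Over 84 elapsed days |
|---|---|---|
| No interruption | 7,840/84 = 93.3 mg/day | 93.3 mg/day |
| 14 of the 120 mg days lost | 6,160/70 = 88.0 | 6,160/84 = 73.3 |
| 14 of the 80 mg days lost | 6,720/70 = 96.0 | 6,720/84 = 80.0 |

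In the last row, the interruption raises dose intensity above the uninterrupted value.

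**The case against.** The strongest reply is that little depends on these measures. No decision rule uses dose intensity. Atezolizumab compliance is the amount given over the amount due, which for 8 of 12 infusions is 6,720/10,080 = 66.7%, the figure said to be missing. SAP 7.3.1 also reports cumulative dose, counts of subjects with interruptions, and a listing. All of this stands, and it confines the point to the descriptive tables.

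A second reply is that the 1400% stacks several readings. The factor of 14 makes sense only with elapsed time, so the authors may have meant to subtract interruptions alone. On that reading the 1400% and the 91-infusion figure disappear. That is fair, but the measure is not rescued: it gives 108% on schedule and 113% with four infusions skipped.

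Third, exposure net of off-drug days is a coherent definition for gilteritinib, and dose intensity still falls when the dose is reduced. Both are true. What remains is that two measures listed separately are the same number, and that interruptions do not register properly.

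Fourth, SAP 7.3.1 does not say for which drug the duration bands are tabulated. The band example therefore applies if atezolizumab is banded, which the per-drug definition in SAP 6.5 suggests.

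Fifth, a narrower fix would give dose intensity its own elapsed-time denominator and leave duration alone. That would correct dose intensity, but atezolizumab duration would still read 12 days after 155 days of treatment.

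**Conclusion.** The point holds. Followed exactly, SAP 6.5 makes duration of exposure equal to the number of dosing days for both drugs. Gilteritinib dose intensity is then algebraically the same as average daily dose. Atezolizumab RDI is the same for every subject given the full assigned dose at each infusion, whether or not infusions are skipped: 1400% under one closing of the bracket and 100% under the other. A part-delivered infusion would still lower it.

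The 1400% and 100% levels depend on the assumed planned intensity; the failure to respond to skipped infusions does not. No other section of either document corrects the formula. The damage is limited to the descriptive tables of duration, duration bands, dose intensity and RDI. It should be corrected before those tables are produced, but it does not touch the efficacy test or the safety monitoring rule.

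**What to change.** Amend SAP 6.5 as follows:

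1. Define duration separately for each drug as elapsed time, with no off-drug days subtracted. Atezolizumab: last infusion date − first infusion date + 14. Gilteritinib: last dose date − first dose date + 1.
2. Write atezolizumab dose intensity as (cumulative dose/duration of exposure)×14, in mg per 14 days.
3. Define planned dose intensity as the assigned starting dose per 14 days (atezolizumab) or per day (gilteritinib).
4. Keep the number of dosing days only as the denominator of average daily dose.

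Full dosing on schedule then gives an RDI of 100% for both drugs (atezolizumab: 840k/(14k)×14 = 840 mg per 14 days).

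The cost is SAP wording and a small derivation change on data already collected. There are two minor drawbacks, which a table footnote should state. Adding 14 days credits a full interval to a subject who dies or stops within 14 days of the last infusion, and an interruption that ends in discontinuation is not counted.

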- r. Only SAE data that is possibly or probably related to study drug will be collected. Any concomitant medications related to SAEs will be collected.
- s. Includes medications taken within 28 days prior to day 1.
- t. Gilteritinib is taken once daily at home except for clinic days when it will be taken at the clinic.
- u. Subject diary for gilteritinib is to be given to the subject on day 1 of every cycle. Subjects should complete as instructed.

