5.1.4 Previous and Concomitant Treatment (Medication and Non-Medication Therapy)

All medications and concomitant treatments administered from 28 days prior to cycle 1/day 1 through the EOT Visit must be recorded in the electronic case report form (eCRF).

Concomitant medications should be collected for reported or ongoing AE/serious adverse events (SAEs) through 30 days after the last dose of study drug for subjects who have discontinued treatment. For subjects who undergo HSCT, concomitant medications should be collected for reported or ongoing AE/SAEs through start of conditioning treatment or 30 days after the last dose of study drug, whichever comes first. Treatment with concomitant drugs that are strong inducers of CYP3A are prohibited. Treatment with concomitant drugs that are strong inhibitors or inducers of P-gp and concomitant drugs that target serotonin 5HT_{2B}R or sigma nonspecific receptor are to be avoided with the exception of drugs that are considered absolutely essential for the care of the subject. Treatment with concomitant drugs that are strong inhibitors of CYP3A should be avoided with the exception of antibiotics, antifungals and antivirals that are used as standard of care to prevent or treat infections. If CYP3A inhibitors are used concomitantly, subjects should be closely monitored for AEs.

Precaution should be used in use of gilteritinib with concomitant drugs that are known to prolong QT or QTc intervals.

Precaution should be used in use of gilteritinib with concomitant drugs that are substrates of BCRP, since the transporter has been shown to be inhibited by gilteritinib in in vitro studies.

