7.2.2 Protocol Deviations

Protocol deviations as defined in the study protocol (Section 8.3 Major Protocol Deviations) will be assessed for all subjects allocated to treatment. The number and percentage of

subjects meeting any criteria will be summarized for each criterion and overall as well as by study site. Subjects deviating from a criterion more than once will be counted once for the corresponding criterion. Any subjects who have more than one protocol deviation will be counted once in the overall summary. A data listing will be provided by site and subject.

The protocol deviation criteria will be uniquely identified in the summary table and listing. The unique identifiers will be as follows:

- PD1 - Entered into the study even though they did not satisfy entry criteria,
- PD2 - Developed withdrawal criteria during the study and was not withdrawn,
- PD3 - Received wrong treatment or incorrect dose,
- PD4 - Received excluded concomitant treatment.

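### The SAP starts the concomitant-medication window 28 days before the first dose, so recorded drugs stopped before treatment are counted as concomitant

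*SAP*

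**What the plan says.** SAP 6.5 (Other Variables) gives two definitions and two dates.

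- Previous: "Previous medication is defined as medication with at least one dose taken before the date of the first dose of study drug". There is no lower date limit, and a drug can be both previous and concomitant.
- Concomitant: "Concomitant medication is defined as medication with at least one dose taken between the date of first exposure (inclusive") and the date of last exposure of study drug, also inclusive.
- Start of the window: "The first exposure is from 28 days prior to cycle 1 day 1".
- End of the window: "The last exposure date is max (the last dosing date for study drug, initial dosing date of the last cycle + 30").

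Protocol 5.1.4 sets the recording period: "All medications and concomitant treatments administered from 28 days prior to cycle 1/day 1 through the EOT Visit must be recorded" in the eCRF. Footnote s to the schedule of assessments, identical in protocol and SAP, gives the same look-back for the row on prior and concomitant medications: "Includes medications taken within 28 days prior to day 1".

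SAP 7.2.4 summarises previous and concomitant medications for the safety analysis set by ATC level and WHO name. It adds no date restriction of its own.

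**The concern.** The definition refers to exposure to study drug, but the sentence that supplies the start date puts it four weeks before any study drug is given. Day -28 is the start of data collection, and it appears to have been carried over into an analysis definition.

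A drug stopped on day -20 would then appear in the concomitant table. Such drugs are foreseeable: screening runs from day -14 to day -1, and inclusion criterion 1 allows for prohibited drugs being stopped after consent.

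Readers use a concomitant-medication table to see what was taken alongside study treatment. That matters here because protocol 1.2.3.2 reports gilteritinib exposure about 70% lower with a strong CYP inducer and about 2.21-fold higher with a strong CYP3A4 inhibitor. A table that also holds drugs stopped before day 1 cannot, on its own, tell a reader which ones overlapped with treatment.

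**Working it through.** The plan states no figure here, so the check is a comparison of date windows.

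**Set-up.** Let day 0 be the date of first dose (cycle 1 day 1), *s* and *e* the first and last day on which a drug was taken (continuous use assumed), and *L* ≥ 0 the last exposure date.

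| Class | Condition | Source |
|---|---|---|
| Recorded | *e* ≥ -28 | Protocol 5.1.4; schedule footnote s |
| Previous | *s* < 0 | SAP 6.5 |
| Concomitant, as written | *e* ≥ -28 and *s* ≤ *L* | SAP 6.5 |
| Concomitant, from first dose | *e* ≥ 0 and *s* ≤ *L* | SAP 6.5 with the start corrected |

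**Step 1: overlap under the written rule.** A drug that is recorded and previous has *e* ≥ -28 and *s* < 0 ≤ *L*. Both conditions for concomitant are met automatically. The inclusion is complete because recording and the concomitant window share the same lower limit.

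**Step 2: which part of the overlap is wrong.** The written and corrected rules differ only for -28 ≤ *e* ≤ -1, that is, for drugs whose last dose fell before the first dose of study drug. For *e* ≥ 0 they agree.

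**Step 3: enumeration as a check.** Take all whole-day intervals with *s* and *e* between -60 and 60, and *L* = 60.

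- Stopped before first dose and recorded (*e* from -28 to -1, *s* from -60 to *e*): 33 + 34 + … + 60 = 28 × 46.5 = 1,302. Concomitant as written: 1,302. Concomitant from first dose: 0.
- Started before and continued past first dose (60 starts × 61 stops): 3,660. Concomitant under both rules: 3,660.
- All recorded previous intervals: 1,302 + 3,660 = 4,962. Concomitant as written: 4,962.
- Last dose before day -28: 1 + 2 + … + 32 = 528. Concomitant as written: 0. The protocol does not ask for these to be recorded.

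The counts depend on the illustrative grid and estimate nothing about the trial. The complete inclusion in step 1 and the affected range in step 2 do not depend on it.

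**Step 4: does another part of the SAP restore a first-dose start?**

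- In the same section, duration of exposure is the last dose date minus "Date of first dose + 1", less days without drug. Exposure there starts at first dose.
- The rules in SAP 7.11.1 for imputing partial start dates of concomitant medications also turn on whether dates fall before or on/after first dose.
- SAP 7.2.4, which specifies the tables, is silent.

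The first two show that first dose is the boundary used elsewhere. None of the three overrides the sentence in 6.5.

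**The case against.** The strongest reply is that this is a misplaced sentence. The definition already speaks of exposure to study drug, so a sensible programmer would start at first dose and treat day -28 as the collection look-back. That probably describes the intent. It does not settle the matter: the sentence stands next to the operative rule for the last exposure date, and a programmer working from the text would implement both.

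The second reply is that little depends on it. This largely stands. The SAP plans no analysis by CYP3A inhibitor, QT-prolonging drug or corticosteroid use, and it has no subgroups (7.8). The concomitant table would still contain every drug taken with study treatment, with extras added. SAP 7.11.1 provides for listings that show actual dates, so a reader could pick out drugs that stopped early.

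Three stronger readings are tempting, and the documents do not support them.

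- *Drugs stopped before day 1 would become protocol deviations* under "PD4 - Received excluded concomitant treatment". Nothing derives this criterion from the 6.5 flag. SAP 7.2.2 takes deviations from protocol 8.3, where they are identified for an individual subject and followed up by the sponsor with the investigator. Protocol 5.1.4 bars other AML treatment while the subject is on gilteritinib, so AML therapy that ended before day 1 does not breach that rule.
- *The previous and concomitant tables overlap by 100%, so all of the overlap is error.* The inclusion is complete, but it contains drugs continued past first dose, which belong in both tables. It is not an error rate.
- *Every earlier drug known to the trial is affected.* Prior FLT3 inhibitor use is a separate baseline item (SAP 7.2.3). A drug last taken before day -28, if a site entered it, would be previous only.

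**Conclusion.** Wrong as written, and minor. The start date in SAP 6.5 contradicts the definition it completes and the duration-of-exposure formula in the same section. Followed literally, it classes as concomitant every recorded drug whose last dose fell between day -28 and the day before first dose.

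The number of such drugs cannot be derived from the documents. It could be small or, given a four-week look-back in relapsed or refractory AML, appreciable. The affected output is the descriptive concomitant-medication summary for the safety analysis set. The CRc test and its confidence interval, the DLT assessment and the sample size are unaffected.

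This conclusion assumes that the tables are programmed from the 6.5 text and that sites record medications over the protocol window.

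**What to change.** In SAP 6.5, replace the sentence on first exposure with: *The first exposure date is the date of the first dose of gilteritinib or atezolizumab, whichever is earlier.* State separately that day -28 is only the start of collection for previous medications. The definition of previous medication can stay, as can the overlap for drugs continued past first dose. The deviation criteria need no change.

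The cost is one sentence and one programming flag. No new data are needed, and the change can be made in a SAP revision before database hard lock, which SAP section 1 allows.
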